14.0 Body Fluid Biospecimens

14.1 Summary Table of Research Blood/Blood Products to Be Collected for This Protocol

NOTE: Please refer to study specific Laboratory Manual.

Indicate if specimen is mandatory or optional	Collection tube description and/or additive (color of tube top)	Volume to collect per tube (number of tubes to be collected)	Blood product being processed and submitted by participating site	Prior to Treatment Initiation ³	Cycle 3, Day 1, Cycle 7, Day 1, Cycle 19 day 1, and at PD, study completion, or time of withdrawal or removal	Cycle 7, Day 1	Additional processing required at site after blood draw?	Storage /shipping conditions ¹
Mandatory (Cohort 1)	BD Vacutainer Cell Preparation Tube with sodium citrate (CPT; light blue/black)	8 ml; up to 24 ml total (3)	PBMC ²	X	X		Yes, Process within 2 hours of collection	Frozen/Dry Ice or Cryopreservation /Liquid Nitrogen
Mandatory (Cohort 2)	BD Vacutainer Cell Preparation Tube with sodium citrate (CPT; light blue/black)	8 ml; up to 24 ml total (3)	PBMC ²	X			Yes, Process within 2 hours of collection	Frozen/Dry Ice or Cryopreservation /Liquid Nitrogen
Mandatory (Cohorts 1	BD Vacutainer	7.5 ml (1)	Serum	X		X	Yes, Process	Frozen/Dry ice

Indicate if specimen is mandatory or optional	Collection tube description and/or additive (color of tube top)	Volume to collect per tube (number of tubes to be collected)	Blood product being processed and submitted by participating site	Prior to Treatment Initiation³	Cycle 3, Day 1, Cycle 7, Day 1, Cycle 19 day 1, and at PD, study completion, or time of withdrawal or removal	Cycle 7, Day 1	Additional processing required at site after blood draw?	Storage /shipping conditions¹
and 2)	Serum Separator Tube (SST; red/gray)						within 2 hours of collection	

1. Kits should be ordered using the Biospecimen Kit Order Form found on the ACCRU web site. After all samples have been processed according to kit instructions, ship all specimens according to shipping instructions (see Section 14.215 and Laboratory Manual for detailed shipping instructions.)
2. Individual sites will run a density gradient with Ficoll-Hypaque gradient that is supplied in the Cell Preparation Tubes (CPT). This will give a PBMC layer in each of the 3 tubes that can be combined in the same cryopreservation tubes.
3. Mandatory blood draw is collected once any time after study registration. For new patients, it must be drawn prior to the study treatment initiation. For patients who have started treatment, it must be drawn at the next treatment visit. Submit the Specimen Submission: Blood (PBMC for Cohort 2 only) form for this blood draw in Rave via Add Event drop down box.

14.2 Study Methodology and Storage Information

14.21 Blood/blood product samples will be collected for the following research

NOTE: research blood samples should not be collected and submitted until *after* the patient is registered onto the study, but *prior* to beginning study treatment.

14.211 The peripheral blood mononuclear cells (PBMC) will be isolated by density gradient from approximately 24ml peripheral blood. In Cohort 1, Samples will be collected before treatment, Cycle 3 Day 1, Cycle 7 Day 1 and Cycle 19 Day 1, or time of withdrawal or removal. In Cohort 2, a single blood draw will be performed pretreatment or at any point during the study in order to generate a source of normal DNA. PBMC will be washed and cryopreserved for later analysis by flow cytometry and as a source of normal control DNA. Cells will be aliquoted in cryopreservation media, frozen at -80°C and shipped overnight on dry ice. For long-term storage, frozen cells will be stored in liquid nitrogen and shipped on liquid nitrogen. (See Laboratory Manual, Cohort 1)

14.212 Serum will be isolated from blood for analysis of TPO and Tg autoantibody levels. Samples will be collected before treatment and on Day 1 of Cycle 7. Autoantibody levels will be run at the University of Colorado Hospital (UCH) providing uniform testing in a CLIA accredited clinical laboratory. The Siemens ADVIA Centaur XP anti-TPO assay at UCH has an analytical sensitivity of 28 U/mL and a dynamic range of 28–1300 U/mL. The Beckman Coulter Access Thyroglobulin Antibody II assay at UCH has an analytical sensitivity of 0.9 IU/mL and a dynamic range of 0.9-2500 IU/mL. Baseline autoantibody status (positive or negative) and titer as well as autoantibody level changes over the treatment period will be correlated with response to therapy. Serum will be isolated from 7.5 mL of blood, aliquoted into 4 cyrovials, and frozen at -80°C for 48 hours before shipping overnight on dry ice (See Laboratory Manual, Cohorts 1 and 2)

14.213 DNA and RNA will be extracted from peripheral blood to generate a baseline control for the studies detailed in Section 17. Remaining DNA and RNA will be stored frozen at -80°C at the University of Colorado, according to patient consent information (see Section 6.12) until specific analyses are identified. As protocols are developed, they will be presented for ACCRU, ITOG, and IRB review and approval. (This collection is part of a general strategy of investigation for the majority of ACCRU studies.)

14.214 As part of ongoing ACCRU research, remaining serum will be stored frozen at -80°C at University of Colorado, according to patient consent information (See Section 6.15) for future studies until specific analyses are identified. As protocols are developed, they will be presented for ACCRU, ITOG and IRB review and approval.

14.215 Shipment of samples: Please refer to the Laboratory Manual.

14.3 Return of Genetic Testing Research Results

Because the results generated by the genetic testing included in this section are not currently anticipated to have clinical relevance to the patient or their family members, the genetic results will not be disclosed to the patients or their physicians.

If at any time, genetic results are obtained that may have clinical relevance, IRB review and approval will be sought regarding the most appropriate manner of disclosure and whether or not validation in a CLIA-certified setting will be required. Sharing of research data with individual patients should only occur when data have been validated by multiple studies and testing has been done in CLIA-approved laboratories.

15.0 Drug Information

IND #132069

15.1 Lenvatinib (LENVIMA®)

- Investigator brochure is available on the ACCRU web site.

15.11 **Background:** Lenvatinib is an oral, multiple receptor tyrosine kinase (RTK) inhibitor that selectively inhibits the kinase activities of vascular endothelial growth factor (VEGF) receptors VEGFR1 (FLT1), VEGFR2 (KDR), and VEGFR3 (FLT4), in addition to other proangiogenic and oncogenic pathway-related RTKs including fibroblast growth factor (FGF) receptors FGFR1, 2, 3, and 4; the platelet derived growth factor (PDGF) receptor PDGFR α ; KIT; and RET.

15.12 **Formulation:** Lenvatinib is available as 1 mg, 4 mg and 10 mg capsules. The following are inactive ingredients: Calcium Carbonate, USP; Mannitol, USP; Microcrystalline Cellulose, NF; Hydroxypropyl Cellulose, NF; Hydroxypropyl Cellulose (type H), NF; and Talc, USP. The hypromellose capsule shell contains titanium dioxide, ferric oxide yellow, and ferric oxide red. The printing ink contains shellac, black iron oxide, potassium hydroxide, and propylene glycol.

15.13 **Preparation and storage:** Store at controlled room temperature, 25 degrees C (77 degrees F), with excursions permitted between 15 and 30 degrees C (59 and 86 degrees F).

15.14 **Administration:** Take lenvatinib at the same time each day with or without food. The capsules should be swallowed whole with water. If a patient misses a dose, and it cannot be taken within 12 hours, then that dose should be omitted and the next dose should be taken at the usual time of administration.

Alternatively, add the lenvatinib capsules to a tablespoon of water or apple juice in a small glass to produce a suspension. Leave the capsules in the liquid for at least 10 minutes. Stir for at least 3 minutes. Drink the mixture. After drinking, add the same amount (1 tablespoon) of water or apple juice to the glass. Swirl the contents a few times and swallow the additional liquid.

This can also be administered by gastric feeding tube.

15.15 **Pharmacokinetic information:**

Absorption: Lenvatinib is rapidly absorbed after oral administration with t_{max} typically observed from 1 to 4 hours post dose. Food does not affect the extent of absorption, but slows the rate of absorption. When administered to healthy subjects with food, peak plasma concentrations are delayed by 2 hours.

Distribution: In vitro binding of lenvatinib to human plasma proteins is high and ranged from 98% to 99% (0.3 – 30 µg/mL, mesilate). This binding was mainly to albumin with minor binding to α1-acid glycoprotein and γ-globulin. In vitro blood to plasma ratios of lenvatinib (0.1 - 10 µg/mL) remained constant in humans (0.589 – 0.608).

Metabolism: Lenvatinib is extensively metabolized in humans. The main metabolic pathways in humans were identified as oxidation by AO, demethylation via CYP3A4, glutathione conjugation with elimination of the O-aryl group (chlorbenzyl moiety), and combinations of these pathways followed by further biotransformations (eg, glucuronidation, hydrolysis of the glutathione moiety, degradation of the cysteine moiety, and intramolecular rearrangement of the cysteinylglycine and cysteine conjugates with subsequent dimerization).

Half-life elimination: Plasma concentrations decline bi-exponentially following C_{max}. The terminal exponential half-life of lenvatinib is about 28 hours.

Excretion: Following administration of radiolabeled lenvatinib to 6 subjects with solid tumors, approximately two-thirds and one-fourth of the radiolabel were eliminated in the feces and urine, respectively.

Special populations: No dose adjustments are required on the basis of hepatic function in patients with mild (Child-Pugh A) or moderate (Child-Pugh B) hepatic impairment. In patients with severe (Child Pugh C) hepatic impairment, the starting dose should be lowered. No dose adjustments are required on the basis of renal function in patients with mild or moderate renal impairment. In patients with severe renal impairment, the starting dose should be lowered. Further dose adjustments may be necessary on the basis of individual tolerability.

15.16 **Potential Drug Interactions:** In vitro, cytochrome P450 3A4 was the predominant (>80%) cytochrome isoform involved in the P450-mediated metabolism of lenvatinib. In vivo, inducers and inhibitors of CYP3A4 had a minimal effect on lenvatinib exposure. Lenvatinib is not considered a strong inducer or inhibitor of cytochrome P450 or uridine 5'-diphospho-glucuronosyl transferase (UGT) enzymes. Lenvatinib may be co-administered without dose adjustment with CYP3A, P-glycoprotein (P-gp), and BCRP inhibitors or CYP3A and P-gp inducers.

15.17 **Known potential toxicities:**

Common and less common known potential toxicities, ≥ 1%

Gastrointestinal: Abdominal pain, diarrhea, diarrhea nausea, vomiting,
 General and administrative site conditions: Asthenia
 Metabolism and nutrition disorders: Decreased appetite, dehydration
 Renal and urinary disorders: Acute kidney injury
 Respiratory thoracic, and mediastinal disorders: Pulmonary embolism
 Vascular disorders: Hypertension, hypotension

Rare known potential toxicities, <1% (Limited to important or life-threatening):

Blood and lymphatic disorders: Thrombocytopenia
 Cardiac disorders: Acute myocardial infarction, cardiac failure, congestive cardiac failure, coronary artery occlusion, left ventricular dysfunction, myocardial infarction
 Endocrine disorders: hypothyroidism
 Gastrointestinal: Abdominal pain lower, abdominal pain upper, anal fistula, constipation, diverticular perforation, intestinal perforation, pancreatitis, acute pancreatitis, rectal hemorrhage, rectal perforation, stomatitis, upper gastrointestinal hemorrhage
 General disorders and administration site conditions: Fatigue, malaise, peripheral edema, impaired wound healing
 Hepatobiliary: Cholecystitis, cholecystitis acute, hepatic failure, hepatic function abnormal, hepatitis acute, hyperbilirubinemia, liver injury
 Infections and infestations: Colonic abscess, perineal abscess, urinary tract infection, urosepsis
 Investigations: Alanine aminotransferase increased, aspartate aminotransferase increased, blood bilirubin increased, ejection fraction increased, lipase increased, weight decreased
 Metabolism and nutrition disorders: Hypocalcemia, hypokalemia, hypomagnesemia
 Musculoskeletal and connective tissue disorders: Arthralgia, back pain, musculoskeletal chest pain, musculoskeletal pain, pain in extremity
 Neoplasms benign, malignant and unspecified: intracranial tumor hemorrhage, tumor hemorrhage
 Nervous system: Cerebrovascular hemorrhage, cerebral infarction, cerebrovascular accident, dizziness, hemorrhage intracranial, headache, ischemic stroke, monoparesis, posterior reversible encephalopathy syndrome, subarachnoid hemorrhage, transient ischemic attack
 Renal and urinary disorders: Hematuria, proteinuria, renal failure, renal impairment, renal tubular necrosis, nephrotic syndrome
 Reproductive system and breast disorders: female genital tract fistula, vaginal hemorrhage
 Respiratory, thoracic and mediastinal disorders: Epistaxis, hemoptysis, pulmonary hemorrhage, pneumothorax
 Vascular: Arterial hemorrhage, aortic dissection

- 15.18 **Drug procurement:** Investigational lenvatinib is provided free of charge to patients by Eisai. Each participating ACCRU membership will order a starter supply of lenvatinib from Eisai.

E-mail the Lenvatinib Drug Order Request Form (found on the ACCRU web

site) to the following:

Include amount of drug needed and date your site must receive drug.

NOTE: drug shipments will take 3-4 days from receipt of drug order. No drug shipments are done on weekends or holidays.

Each participating ACCRU treating location will be responsible for monitoring the supply of lenvatinib and will use the drug ordering instructions above to order additional supplies as needed.

Outdated or remaining drug is to be destroyed on-site as per procedures in place at each institution.

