Hemoglobin	≥ 9 g/dL or ≥ 5.6 mmol/L without transfusion or erythropoietin dependency (≤ 7 days prior to registration)
Renal	
Serum creatinine OR Measured or calculated ^a creatinine clearance (GFR can also be used in place of creatinine or CrCl)	≤ 1.5 X upper limit of normal (ULN) OR ≥ 60 mL/min for subject with creatinine levels > 1.5 X institutional ULN
Hepatic	
Serum total bilirubin	≤ 1.5 X ULN OR Direct bilirubin \leq ULN for subjects with total bilirubin levels > 1.5 ULN
AST (SGOT) and ALT (SGPT)	≤ 2.5 X ULN OR ≤ 5 X ULN for subjects with liver metastases
Albumin	≥ 2.5 mg/dL
Coagulation	
International Normalized Ratio (INR) or Prothrombin Time (PT)	≤ 1.5 X ULN unless subject is receiving anticoagulant therapy as long as PT or PTT is within therapeutic range of intended use of anticoagulants
Activated Partial Thromboplastin Time (aPTT)	≤ 1.5 X ULN unless subject is receiving anticoagulant therapy as long as PT or PTT is within therapeutic range of intended use of anticoagulants
^a Creatinine clearance should be calculated per institutional standard.	

- 3.19a Adequately controlled blood pressure with or without antihypertensive medications defined as BP $< 150/90$ mmHg at screening.
- 3.19b Negative pregnancy test done ≤ 7 days prior to registration, for women of childbearing potential only.
- 3.19c Ability to complete Patient Medication and Blood Pressure diaries by themselves or with assistance.
- 3.19d Willing and able to provide informed written consent.

- 3.19e Willing to return to enrolling institution for follow-up (during the Active Monitoring Phase of the study).

*Note: During the **Active Monitoring** Phase of a study (i.e., active treatment and observation), participants must be willing to return to the consenting institution for follow-up.*

- 3.19f Willing to provide tissue and blood samples for correlative research purposes.(see Sections 6.12, 14.1 and 17.11).

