7.0 Protocol Treatment

7.1 Treatment Schedule

Arm	Agent	Dose Level	Route	Day
	Lenvatinib	20 mg	PO	Once daily Days 1 through 21 of each 21-day cycle
	Pembrolizumab	200 mg	IV	Day 1 of each 21-day cycle

7.11 Cohort 1: Lenvatinib-naïve patients will be administered both study drugs (pembrolizumab and lenvatinib) as of Cycle 1 Day 1. Each cycle is 21 days. The starting dose of oral lenvatinib is 20 mg (two 10-mg capsules).

7.12 Cohort 2: Pembrolizumab will be added to the treatment for patients who experience PD on lenvatinib alone. They will remain on or resume the dose of lenvatinib on which they experienced PD. Cycle 1 Day 1 will be the first day pembrolizumab is added to the treatment. Patients who have temporarily stopped lenvatinib dosing within 30 days of enrollment will restart lenvatinib at their prior dose along with pembrolizumab on Cycle 1 Day 1 of treatment. Patients entering Cohort 2 will have progressed on lenvatinib. These patients will remain on the dose they are taking at the time of study entry, which may have been previously reduced for side effect management, and will not exceed 20 mg by mouth daily.

- 7.2 Patients will be instructed on lenvatinib administration, to be taken with water orally once a day (with or without food) at approximately the same time each day, and granted treatment independence with nursing staff approval. If a patient misses a dose, and cannot be taken within 12 hours, then that dose should be omitted and the next dose should be taken at the usual time of administration. If a patient vomits after taking the daily dose of lenvatinib, DO NOT repeat dosing. Resume regular dosing the next day. NOTE: The patient will be requested to maintain a medication diary to document time and date when each dose of lenvatinib is taken. Patient will also document number of pills/dose of medication taken, and note any vomiting subsequent to dosing. The medication diary will be returned to clinic staff at each examination visit (see Section 4.0).
- 7.3 Pembrolizumab, 200 mg, will be administered as a 30-minute IV infusion every 21 days (treatment cycle intervals may be increased based on toxicities as described in section 8.3). Sites should target infusion timing to be as close to 30 minutes as possible, however, given the variability of infusion pumps from site to site, a window of -5 and +10 minutes is permitted (i.e., infusions lasting between 25 minutes to 40 minutes are acceptable).

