8.1 Dose Levels (Based on Adverse Events in Tables 8.2 and 8.3)

Dose Level	Lenvatinib ^a	Pembrolizumab
0 ^b	20 mg orally once a day	200 mg IV every 21 days
-1	14 mg orally once a day	No dose reduction allowed
-2	10 mg orally once a day	No dose reduction allowed
-3	4 mg orally once a day	No dose reduction allowed

^a Once the dose has been reduced, it should not be increased at a later date.

^b Dose level 0 refers to the starting dose.

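### The albumin floor in 3.18 is printed in mg/dL and so excludes nobody; separately, and minor, 7.11 does not carry over the 15.15 instruction to lower the lenvatinib start in severe renal impairment

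*Combined protocol and SAP*

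**What the plan says.** **Albumin.** The laboratory table in 3.18 requires albumin of at least 2.5 mg/dL. Hemoglobin, in the same table, is given in g/dL. The head of section 3.0 allows no eligibility waivers.

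**Renal function at entry.** 3.18 accepts serum creatinine up to 1.5 x ULN on its own. The clearance alternative is "≥ 60 mL/min for subject with creatinine levels > 1.5 X institutional ULN", so it applies only above that cap. The table adds "GFR can also be used in place of creatinine or CrCl", which is an option and not a requirement. Footnote a says "Creatinine clearance should be calculated per institutional standard". Age has a lower limit of 18 and no upper limit (3.11).

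**Lenvatinib dose.** For Cohort 1, 7.11 says "The starting dose of oral lenvatinib is 20 mg (two 10-mg capsules". Table 8.1 calls this level 0; its lower levels (14, 10 and 4 mg) are tied to adverse events. The special-populations text in 15.15 says "No dose adjustments are required on the basis of renal function in patients with mild or moderate renal impairment", and then "In patients with severe renal impairment, the starting dose should be lowered". It does not define severe or give the lower dose. Section 15.1 notes "Investigator brochure is available on the ACCRU web site".

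**The concern.** The albumin line is an operative eligibility rule with a wrong figure. Read literally, it screens out no patient, however low the albumin. Sites must then guess the intended unit in a protocol that permits no waivers.

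The renal instruction sits in a pharmacokinetics paragraph and appears in neither 3.18 nor 7.11, the sections from which sites enrol and dose. An investigator who follows 15.15 departs from 7.11 without a protocol dose to use; one who follows 7.11 gives 20 mg to a patient for whom 15.15 asks for less. The drug's listed toxicities at 1% or more include acute kidney injury (15.17). The question is whether 3.18 can admit such a patient at all.

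**Working it through.** The plan gives no figure on either point to reproduce.

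**1. Albumin.** 1 g = 1,000 mg.
- Printed floor: 2.5 mg/dL ÷ 1,000 = 0.0025 g/dL.
- Evident intention: 2.5 g/dL = 2,500 mg/dL, which is 1,000 times higher.
- Test case: a patient at 1.5 g/dL has 1,500 mg/dL. This passes the printed floor (1,500 > 2.5) and fails the intended one (1,500 < 2,500).

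**2. Can 3.18 admit a patient with severe renal impairment?**

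Inputs from the documents: the cap of 1.5 x ULN, the 20 mg start, no upper age limit, and at most 30 Cohort 1 patients (16.21).

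Assumptions, not in the documents: severe means clearance below 30 mL/min; creatinine ULN is 1.0–1.1 mg/dL for women (cap 1.50–1.65) and 1.2–1.3 for men (cap 1.80–1.95). The two equations below are standard and are not named in the protocol.

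- Cockcroft-Gault = (140 − age) × weight ÷ (72 × creatinine), × 0.85 for women.
- CKD-EPI 2021 at these creatinine values = 142 × (creatinine/k)^−1.2 × 0.9938^age, × 1.012 for women, with k = 0.7 (women) or 0.9 (men).

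| Patient at the cap | Cockcroft-Gault | CKD-EPI |
|---|---|---|
| Woman, 75 y, 55 kg, 1.50 mg/dL | 65 × 55 × 0.85 ÷ (72 × 1.50) = 28.1 | 36.1 |
| Woman, 80 y, 60 kg, 1.65 mg/dL | 60 × 60 × 0.85 ÷ (72 × 1.65) = 25.8 | 31.2 |
| Man, 80 y, 65 kg, 1.95 mg/dL | 60 × 65 ÷ (72 × 1.95) = 27.8 | 34.1 |

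All three enter under 3.18 on creatinine. All are below 30 by one formula and above 30 by the other.

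**3. How far does this depend on the assumptions?** The age above which Cockcroft-Gault at the cap falls below the cut-off is 140 − cut-off × 72 × creatinine ÷ weight, with weight × 0.85 for women.

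| Cut-off (mL/min) | Woman, 55 kg | Woman, 60 kg | Man, 65 kg |
|---|---|---|---|
| 30 | 63.8–70.7 | 70.1–76.5 | 75.2–80.2 |
| 25 | 76.5–82.2 | 81.8–87.1 | 86.0–90.2 |
| 20 | 89.2–93.8 | 93.4–97.6 | 96.8–100.1 |

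- Weight: for a 70 kg woman the age for the 30 cut-off rises to 80.1–85.5.
- ULN: with a female ULN of 0.9 (cap 1.35), the first example becomes 65 × 55 × 0.85 ÷ (72 × 1.35) = 31.3, no longer below 30.
- Formula: CKD-EPI at the assumed caps, ages 60–85, runs from 30.3 to 42.6. It drops below 30 only outside that range, for example 29.9 for a woman of 87 at 1.65 mg/dL, or 29.9 at age 70 if the female ULN is 1.2 (cap 1.80).

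**4. How many patients?** This cannot be derived, because the documents give no distribution of age, weight or creatinine. Low weight, higher age and creatinine near the cap must coincide, so none or very few of at most 30 is a judgment.

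**The case against.** **15.15 is itself protocol text.** It can be read as a specific exception to the general start in 7.11, and nothing in 7.11 or Table 8.1 overrides it. This stands: a reader might infer that the protocol contradicts itself or orders unsafe dosing, and the documents do not support that. What remains is an instruction without a cut-off or dose, placed away from the dosing section. The brochure may supply both.

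**20 mg may already be a lowered start.** Section 1.8 gives 24 mg as the approved starting dose. But it attributes the 20 mg to a recommendation for the combination, not to renal function, and every Cohort 1 patient gets it. This reading is possible and unsettled.

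**The conflict rests on outside figures.** This stands too. With a cut-off of 20 mL/min almost nobody is affected, and 15.15 does not say that Cockcroft-Gault is the relevant measure. A reader might therefore want a mandatory Cockcroft-Gault floor in 3.18. The documents do not support one: 15.15 asks for a lower dose, not exclusion, and footnote a leaves the formula to the institution.

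**Safeguards exist.** Investigators may decline a patient before the first dose (3.26, 3.29k); proteinuria above 1 g/24 h excludes (3.29p); acute kidney injury is graded at baseline and each evaluation (10.52); renal function is monitored (15.199); Grade 3 toxicity requires interruption (8.2). These limit harm, but none sets a clearance threshold or a lower starting dose.

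**The albumin unit is an obvious slip.** Sites that report in g/dL would probably apply 2.5 g/dL. That limits the consequence, but the printed rule is still wrong.

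**Conclusion.** The albumin floor in 3.18 is wrong as written, and this needs no assumption. It is out by a factor of 1,000 and excludes nobody. The documents do not show that any patient with low albumin was or would be enrolled because of it.

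The renal point is a minor gap in drafting, confined to Cohort 1. It becomes a real conflict only if severe means below about 30 mL/min, the site admits on creatinine, clearance is judged by Cockcroft-Gault, and 15.15 means a start below 20 mg. Cohort 2 keeps its entry dose, up to 20 mg (7.12), and is outside this point. A reader might infer an effect on the complete response decision from either point; nothing in the documents supports that, and none is claimed. The albumin error does not make the renal point more serious.

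**What to change.** 1. In 3.18, change the albumin floor to 2.5 g/dL. This is a unit correction and costs nothing.
2. In 7.11, add one sentence for Cohort 1 that refers to 15.15 and states the cut-off for severe renal impairment, the formula and the reduced starting dose. The sponsor should take all three from the investigator brochure, since the protocol supplies none of them. The formula needs naming because the three example patients fall on different sides of 30 mL/min depending on it.

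Do not add a Cockcroft-Gault exclusion floor to 3.18.

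The second change needs no new type of test: the usual formulas use creatinine, age, sex and, for Cockcroft-Gault, weight. The patient medication diary prints two 10-mg capsules a day, so the copy given to a patient on a reduced start would need the right dose. The only other cost is that a rare patient starts lower. No sample size, power or significance figure changes.
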